1.2 Study Agent(s)/Devices Background and Associated Known Toxicities

Misoprostol is an analogue of prostaglandin E1 initially developed for treatment of NSAID induced peptic ulcers, which is currently used in a variety of contexts in the field of obstetrics and gynecology including in the FDA approved regimen for medical abortion, cervical ripening, and treatment of postpartum hemorrhage. In non-pregnant women, misoprostol has been widely described for use in cervical preparation prior to hysteroscopy, intrauterine device insertion, and endometrial biopsy.

Multiple routes of administration have been studied including oral, sublingual or buccal, rectal and vaginal administration with peak plasma concentrations less than 30 minutes after administration via the oral or sublingual route. Systemic bioavailability of sublingual misoprostol is significantly greater than with orally or vaginally administered misoprostol however overall plasma concentrations persist for at least 6 hours at higher concentrations when administered vaginally. Potent uterotonic activity is noted as a result of increased intracellular calcium activating myosin light-chain kinase.

Adverse effects of misoprostol vary and include abnormal vaginal bleeding, lower abdominal pain and cramping, fever or shivering, nausea, vomiting and diarrhea with more uterine cramping and vaginal bleeding associated with vaginal administration (3).

Prior studies evaluating misoprostol effect on intraoperative blood loss at time of either an abdominal and laparoscopic myomectomy have used a single dose of 400mcg misoprostol administered vaginally or rectally pre-procedure and have found a significant decrease in blood loss. 400mcg is the standard dose used for the majority of gynecologic applications and appears to be well tolerated (4-9). There are no additional risks to study participants adding laparoscopic surgery to this study.

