2.2 Secondary Objectives

2.2.1 To determine the effect of 400mcg buccal misoprostol at least one hour pre-procedure on the need for blood transfusion during or in post-operative course for either an abdominal or laparoscopic myomectomy

2.2.2 To determine the effect of 400mcg buccal misoprostol at least one hour pre-procedure on post-operative fever after either an abdominal or laparoscopic myomectomy.

2.2.3 To determine the incidence of adverse effects, if any, of 400mcg buccal misoprostol at least one hour prior to either an abdominal or laparoscopic myomectomy.

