7.1.4 Adverse Reactions

The FDA reports the following possible side effects with the active medication (Misoprostol):

Gastrointestinal: In subjects receiving Cytotec 400 or 800 mcg daily in clinical trials, the most frequent gastrointestinal adverse events were diarrhea and abdominal pain. The incidence of diarrhea at 800 mcg in controlled trials in patients on NSAIDs ranged from 14-40% and in all studies (over 5,000 patients) averaged 13%. Abdominal pain occurred in 13-20% of patients in NSAID trials and about 7% in all studies, but there was no consistent difference from placebo.

Diarrhea was dose related and usually developed early in the course of therapy (after 13 days), usually was self-limiting (often resolving after 8 days), but sometimes required discontinuation of Cytotec (2% of the patients). Rare instances of profound diarrhea leading to severe dehydration have been reported.

Patients with an underlying condition such as inflammatory bowel disease, or those in whom dehydration, were it to occur, would be dangerous, should be monitored carefully if Cytotec is prescribed.

Gynecological: Women who received Cytotec during clinical trials reported the following gynecological disorders: spotting (0.7%), cramps (0.6%), hypermenorrhea (0.5%), menstrual disorder (0.3%) and dysmenorrhea (0.1%). Postmenopausal vaginal bleeding may be related to Cytotec administration. If it occurs, diagnostic workup should be undertaken to rule out gynecological pathology. Research studies in obstetrics and gynecology also identify possible side effects of diarrhea, fever and shivering (4,6,7).

Elderly: There were no significant differences in the safety profile of Cytotec in approximately 500 ulcer patients who were 65 years of age or older compared with younger patients.

Additional adverse events which were reported are categorized as follows:

In clinical trials, the following adverse reactions were reported by more than 1% of the subjects receiving Cytotec and may be causally related to the drug: nausea (3.2%), flatulence, (2.9%), headache (2.4%), dyspepsia (2.0%), vomiting (1.3%), and constipation (1.1%). However, there were no significant differences between the incidences of these events for Cytotec and placebo.

Causal relationship unknown: The following adverse events were infrequently reported. Causal relationships between Cytotec and these events have not been established but cannot be excluded:

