10.0 STATISTICAL CONSIDERATIONS

10.1 Study Design/Study Endpoints

This is a double blinded randomized, controlled trial of women undergoing either an abdominal and laparoscopic myomectomy at a single university-affiliated tertiary care center. Women ages 18-50 years of age with clinically documented, sonographic evidence of uterine fibroids being scheduled for abdominal myomectomy were eligible for inclusion. Eligible participants will be randomized to receive preoperative 400cg buccal misoprostol or placebo on the basis of total fibroid volume, location (intramural or subserosal) and parity. Stratification by fibroid volume (or fibroid size) will be performed prior to randomization. Fibroid volume is defined as the cumulative volume of intramural and subserosal fibroids as measured on preoperative magnetic resonance imaging (MRI), or in the instance of patient contraindication to MRI, transvaginal ultrasound (TVUS). The data collection sheet (addendum) and chart of study variables below include definition of this variable and allow for ease of recording and tracking of this variable in our study database. Women with a history of gynecologic malignancy, critical anemia or blood dyscrasias and those with a history of prior myomectomies will be excluded.

List of Study Variables to be Collected:

Outcomes	Type	Definition
Estimated blood loss	Continuous	Intraoperative blood loss as estimated by intraoperative anesthesiologists and surgeons.
% drop in Hgb	Continuous	Ratio of the drop in hemoglobin over the starting hemoglobin ($Hg_{post-op} - Hg_{pre-op}$)/ Hg_{pre-op}
Duration of hospital stay (days)	Continuous	Number of days inpatient following abdominal myomectomy.
Duration of procedure (minutes)	Continuous	Number of days inpatient following abdominal myomectomy.
Post-op fever	Dichotomous	If patient has one Temperature >101.4 or two temperatures >100.4 , then yes. If not then no.
Adverse reaction to misoprostol	Dichotomous	If patient experiences vaginal bleeding, vomiting or diarrhea then yes. If not then no.

Exposures	Type	Definition
Pre-op Misoprostol	Dichotomous	If women randomized to receive misoprostol, then yes. If women randomized to placebo, then no.

Covariates	Type	Definition
Woman's Age	Continuous	Female age in years at time of abdominal myomectomy
Volume of fibroids (pre-op)	Continuous	Cumulative volume of intramural and subserosal fibroids based on preoperative imaging Will be used for stratification and randomization.

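### The adverse-reaction outcome counts only vaginal bleeding, vomiting or diarrhea, so shivering, nausea and cramping, which the protocol itself names as misoprostol effects, are not compared between arms

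*Combined protocol and SAP*

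**What the plan says.** Section 2.2, objective 2.2.3, is open-ended: "To determine the incidence of adverse effects, if any, of 400mcg buccal misoprostol". It is not restricted to particular symptoms.

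The outcomes table in section 10.1 turns this into one dichotomous variable, adverse reaction to misoprostol, with the rule "If patient experiences vaginal bleeding, vomiting or diarrhea then yes", and no in every other case. The row states no observation window and requires no attribution to study drug.

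Section 1.2 gives a longer list. The drug's adverse effects "include abnormal vaginal bleeding, lower abdominal pain and cramping, fever or shivering, nausea, vomiting and diarrhea". Section 7.1.4 adds that research studies in obstetrics and gynecology "also identify possible side effects of diarrhea, fever and shivering (4,6,7"; the trailing numbers are literature references.

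Fever has its own row in section 10.1 and its own objective, 2.2.2. Section 7.3.1 defines an adverse event broadly, but section 7.5.2 provides only annual routine reporting for events that do not need expedited reporting. Section 10.3 names no analysis of adverse effects. The Study Summary's general rule, Fisher's exact test for categorical variables, would reach the three-symptom row but not symptoms that are not variables.

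**The concern.** The rule has no residual category: everyone without one of the three symptoms is scored as having had no reaction. A woman who shivers, is nauseated or has cramps after the tablet, and has nothing else, is therefore counted with the unaffected.

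The placebo arm is what separates drug effect from the background of anesthesia and surgery, but it can do so only for symptoms that are compared. A statement about tolerability based on this row would be silent on several effects that the protocol attributes to the drug.

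**Working it through.** **1. Comparing the lists.**

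| Effect named in section 1.2 | Where it is an outcome in section 10.1 |
|---|---|
| Vaginal bleeding | Adverse-reaction row |
| Vomiting | Adverse-reaction row |
| Diarrhea | Adverse-reaction row |
| Fever | Own row |
| Shivering | None |
| Nausea | None |
| Lower abdominal pain and cramping | None |

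The counted symptoms are a strict subset of the section 1.2 list. Whatever the rates, and however the symptoms overlap, the incidence of the defined outcome cannot exceed the incidence of any effect on that list. It is lower whenever at least one woman has only an uncounted effect.

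**2. Can the shortfall be sized?** The documents state no rate or power for this outcome, so there is no planned figure to reproduce. Section 7.1.4 gives label rates from other regimens: spotting 0.7% (taken here as vaginal bleeding), vomiting 1.3%, diarrhea 13% on average (in a sentence about 800 mcg), nausea 3.2% and cramps 0.6%. It gives no rate for shivering, so 5% to 40% is assumed. If symptoms are independent (also an assumption), the chance of at least one is 1 − ∏(1 − pᵢ).

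- Outcome as defined: 1 − 0.993 × 0.987 × 0.87 = 14.7%, about 5.2 of 35 women.
- Adding nausea and cramps: 1 − 0.993 × 0.987 × 0.87 × 0.968 × 0.994 = 18.0%, about 6.3 of 35.
- Adding shivering at 5%, 10%, 20% or 40%: 22.1%, 26.2%, 34.4% or 50.8%.
- Share of affected women captured by the defined outcome: 14.7/22.1 = 67%, falling to 14.7/50.8 = 29%.

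The share depends heavily on the diarrhea rate:

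- At 40%, the top of the NSAID-trial range, the defined outcome is 41.2%. The six-effect figure is 46.3% to 66.0%, so 89% to 62% is captured.
- With no diarrhea, the defined outcome is 2.0%. The six-effect figure is 10.4% to 43.4%, so 19% to 5% is captured.

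A captured share anywhere from about 5% to 89% means that the size cannot be derived from the documents. These figures are not predictions for this trial.

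**3. Which omissions matter most?** Section 7.1.4 reports no consistent difference from placebo for abdominal pain. It reports no significant difference for the group of events that contains both nausea and vomiting. It makes no such statement about shivering, which is named in two sections. Shivering is therefore the omission most likely to hide a difference between arms.

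**The case against.** **The narrow set may be deliberate.** Section 7.7 names nearly the same three events as examples of intolerable side effects, and all three are observable. That is plausible, but the protocol gives no reason. Specificity does not explain the choice: vomiting is counted and nausea is not, although section 7.1.4 treats them alike against placebo, and vaginal bleeding is non-specific after uterine surgery.

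**Section 7 would capture the missing symptoms.** The adverse-event definition is broad enough, events are graded and attributed, and incidence by arm could be tabulated from those records. The data collection sheet is an attachment outside the available text and may already have the items. So one cannot say that the events go unrecorded. What stands is that nothing links such records to objective 2.2.3 or plans a comparison by arm.

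**The omitted events may be less common than they look.** A reader might infer from the 13–20% for abdominal pain that omitted events are as frequent as counted ones. Like for like, diarrhea is the more frequent: 14–40% against 13–20% in NSAID trials, and 13% against about 7% in all studies. Nausea does exceed vomiting (3.2% against 1.3%), but neither figure shows a drug effect.

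**A wider composite could do harm.** This objection is right. Nausea and pain are common after surgery and would be unattributed, so folding them in could turn most women in both arms positive and dilute the contrast. Adding fever would count it in two secondary outcomes.

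**Conclusion.** The concern holds as a mismatch between objective 2.2.3 and the variable that serves it. Three effects named in section 1.2 fall outside every listed outcome, and no planned analysis compares them by arm. This rests on the text alone and needs no assumption about rates.

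Two stronger readings are not supported. The first is that the reported incidence will be too low in absolute terms. The row requires no attribution, so vomiting or bleeding due to anesthesia or surgery also scores as a reaction and the raw rate could be inflated. The count is low only relative to the protocol's own list, and its net direction for true drug effects is unknown. The second is that a known number of reactions, or a known difference between arms, will be missed. With no shivering rate and no rates for this single buccal dose, any such number is an assumption.

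The primary outcome, blood loss, is unaffected.

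**What to change.** In section 10.1, list shivering, nausea and abdominal pain or cramping as separately recorded yes/no symptoms, alongside vaginal bleeding, vomiting and diarrhea. State one observation window that applies equally to both arms.

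In section 10.3, report each of the six symptoms by arm with Fisher's exact test, next to the existing three-symptom composite. Leave that composite as it is: do not fold postoperative pain and nausea into it, and keep fever in its own row. A sentence giving the reason for the three-symptom composite would also help.

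The cost is a few more items to record and several unpowered comparisons, which should be labelled descriptive. For scale, take 35 women per arm and a symptom absent on placebo. Five cases on misoprostol give a two-sided p of 2 × C(35,5)/C(70,5) = 2 × 324,632/12,103,014 = 0.054. Six cases (6/35 = 17%) give 2 × C(35,6)/C(70,6) = 2 × 1,623,160/131,115,985 = 0.025. A non-significant result for any one symptom should therefore not be read as equal tolerability.

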Objectives	Examine efficacy of buccal misoprostol at reduction in intraoperative blood loss at time of either an abdominal and laparoscopic myomectomy
Number of Subjects	70
Diagnosis and Main Inclusion Criteria	Symptomatic uterine fibroids, desire to retain uterus
Study Product(s), Dose, Route, Regimen	Misoprostol 400mcg buccally
Duration of administration	1 hour pre-procedure – At least 4 hours post-procedure
Reference therapy	Placebo (100mg Vitamin B6 tablets)
Statistical Methodology	Power calculation indicates 35 patients per arm will detect 1 standard deviation difference with 90% power. Fisher's exact test to be used for categorical variables and T test to be used for continuous variables with $P <.05$.

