3.1 Inclusion Criteria

- 3.1.1 Patients presenting for either an abdominal and myomectomy with documented uterine fibroids on pelvic imaging (pelvic ultrasound or MRI) within in last 12 months
- 3.1.2 Age \geq 18 years and \leq 50 years.
- 3.1.3 Pre-operative hemoglobin >8 g/dl.
- 3.1.4 Willing to have buccal administration of misoprostol or a placebo at least one hour pre-procedure.
- 3.1.5 Ability to understand and the willingness to sign a written informed consent.
- 3.1.6 Admissible medical/surgical history.
 - a. Can be previously treated with Depo-Lupron, Depo-Provera, or Oral Contraceptive pills
 - b. Intraoperative use of vasopressin and uterine tourniquet is permissible
 - c. Can have had prior Cesarean delivery

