Mass of fibroids (post-op)	Continuous	Cumulative mass of intramural and subserosal fibroids based on pathology reports -Will be used to account for variability in final models.
Pre-treatment with Lupron, Depo-provera, OCPs	Dichotomous	Pre-operative treatment with Lupron, Depo-provera or OCP's
Intraoperative treatment with vasopressin or tourniquet	Dichotomous	Use of intraoperative vasopressin or tourniquet during myomectomy.

Other	Type	Definition	Use
Uterus size in weeks gestation	Ordinal	Uterus size in weeks gestation per pre-operative physical exam	Table 1 characteristic
History of Gynecologic Malignancy	Dichotomous	If history of gynecologic cancer (uterine, ovarian or cervical cancer), then yes. If not, then no.	Exclude if yes.
Uterine Anomaly	Dichotomous	If septate, unicornuate or bicornuate uterus, then yes. If abnormality is less severe than arcuate uterus or normal then no.	Exclude if yes.
Prior Cesarean Section Cycle	Dichotomous	If prior Cesarean delivery, then yes. If no prior Cesarean delivery, then no.	Table 1 characteristic, stratum-specific sub-analyses
Gravidity	Count	Number of prior pregnancies	Table 1 population characteristic
Gravid	Dichotomous	If number of pregnancies is 1+, then yes If number of pregnancies is 0, then no	Table 1 characteristic, stratum-specific sub-analyses
Parity	Count	Number of prior pregnancies	Table 1 population characteristic
Living children	Count	Number of living children	Table 1 characteristic
Woman's Age (SART categories)	Categorical	Group by age in years at abdominal myomectomy: <30 30-34 35-37 38-39 40-42 43+	Table 1 population characteristic
Race	Categorical	Group by race: White, Black/Africa-American, Hispanic, Asian/Pacific	Table 1 population characteristic

		Islander, American Indian/Alaskan Native, Middle-Eastern	
--	--	--	--

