10.2 Sample Size and Accrual

Power calculation based on the standard deviation in published reports (5) demonstrates that enrollment of 25 participants per arm is necessary to detect 1 standard deviation difference with 90% power. Further, published results from pilot studies in this population (7) and demonstrates that enrollment of 25 participants per arm is necessary to detect 0.5g/dL difference in hemoglobin with 90% power.

Prentice Women's Hospital of Northwestern Memorial performed over 100 abdominal myomectomies in 2013. Across a year-long study period, we anticipate identifying a minimum of 70 patients to evaluate our primary hypothesis. We have increased our sample size from 50 to 70 to account for the 9 participants that were either consented by a non-study team member, did not get the study drug due to an error at pharmacy or left the hospital after surgery thus we could not obtain a POD 1 which is needed for data analysis.

Following data collection from at least 20 participants in each arm, standard deviation calculations will be performed to confirm that the standard deviations in our sample population is similar. Power calculation will be repeated using the standard deviations in our active and placebo groups and additional participants will be enrolled as needed to achieve adequate power to evaluate our primary outcome of intraoperative blood loss.

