10.3 Data Analyses Plans

To determine whether women who take a pre-operative dose of misoprostol experience lower blood loss during abdominal myomectomy compared to matched controls who take placebo, we will perform linear regression. We will use this model to assess for the role of numerous covariates, including gravidity, parity and age. Secondary outcomes of percent hemoglobin drop, duration of procedure and length of inpatient hospitalization will be assessed using the T test and further evaluated with multivariate-adjusted linear regression where appropriate. The need for post-operative blood transfusion between groups will be assessed with the Chi-square (Fischer's exact) test. The role of numerous potential covariates will be assessed with Chi-square (Fischer's exact) test for dichotomous variables and T test for continuous variables with $p < 0.05$.

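### Sub-analyses by prior cesarean and gravid status are planned without a test of whether the treatment effect differs between strata

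*Combined protocol and SAP*

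**What the plan says.** In the section 10.1 table of variables, the rows for prior cesarean and for gravid status both give the use as "Table 1 characteristic, stratum-specific sub-analyses". The other patient-characteristic rows in that part of the table (uterus size, gravidity, parity, living children, age group, race) are marked for Table 1 only, so these two factors were singled out. Both have two levels: "If prior Cesarean delivery, then yes. If no prior Cesarean delivery, then no" for the first and "If number of pregnancies is 1+, then yes If number of pregnancies is 0, then no" for the second. Section 3.1 admits women with a previous cesarean ("Can have had prior Cesarean delivery"), so that stratum can be filled.

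Section 10.3 plans a linear regression for blood loss and adds: "We will use this model to assess for the role of numerous covariates, including gravidity, parity and age". That sentence concerns covariates in the overall model. It neither promises nor rules out a treatment-by-covariate term. Section 10.3 does not mention the sub-analyses, an interaction or heterogeneity test, or how stratum results would be interpreted.

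A 0.05 threshold appears in the Study Summary, for Fisher and t tests in general, and in section 10.3, for assessing covariates. Neither place ties it to the strata.

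**The concern.** Separate analyses answer two questions: is there an effect in this stratum, and is there one in that stratum? They do not answer whether the two effects differ, which is usually why a subgroup is examined. The precision of each result depends on the stratum's size. When the true effect is the same in both, one result can pass a significance threshold and the other miss it simply because each stratum holds only part of a 70-patient trial.

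The plan names no other basis for comparing the strata. If each result is judged at 0.05, a report could suggest that misoprostol helps only gravid women, or only women without a prior cesarean, when the data hold no evidence of a difference.

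**Working it through.** **Inputs from the plan.** Total 70, or 35 per arm, with a design effect of 1 SD (Study Summary); threshold 0.05; two levels for each factor (section 10.1).

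**Assumptions.** Two-sided test; 1:1 arms within each stratum; the same true effect d (in SD units) in both strata; equal variances. The documents give no stratum sizes, so splits of 50/50, 25 and 10 per arm, and 80/20 are shown. Effects of 0.75, 0.5 and 0 SD are added for range.

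**Step 1: the plan's own figure.** Section 10.2 states that "enrollment of 25 participants per arm is necessary to detect 1 standard deviation difference with 90% power". Power of a two-sample t test with n per arm comes from the noncentral t distribution with 2n − 2 degrees of freedom and noncentrality d × √(n/2). At d = 1, n = 22 gives 89.97%, so 23 per arm are needed; 25 per arm gives 93.4%. The plan's figure is reproduced within two patients per arm. The summary's 35 per arm gives 98.5%; section 10.2 explains the increase by unusable participants.

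**Step 2: discordant strata.** With power p₁ and p₂ in two independent strata,

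P(exactly one significant) = p₁(1 − p₂) + p₂(1 − p₁).

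At 1 SD with 7 and 28 per arm, the noncentralities are √3.5 = 1.87 and √14 = 3.74, and the powers are 0.406 and 0.957. Then 0.406 × 0.043 + 0.957 × 0.594 = 0.586.

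| True effect in both strata | 17.5 and 17.5 per arm | 10 and 25 per arm | 7 and 28 per arm |
|---|---|---|---|
| 1 SD: power in each | 0.819, 0.819 | 0.562, 0.934 | 0.406, 0.957 |
| 1 SD: exactly one significant | 29.7% | 44.6% | 58.6% |
| 0.75 SD: exactly one significant | 48.8% | 56.9% | 64.2% |
| 0.5 SD: exactly one significant | 42.0% | 44.3% | 46.5% |
| No effect: exactly one significant | 9.5% | 9.5% | 9.5% |

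The last row is 2 × 0.05 × 0.95. Simulation with 40,000 trials per setting agrees: for 7 and 28 per arm it gives 58.7% at 1 SD, 64.2% at 0.75 SD and 46.6% at 0.5 SD.

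**Step 3: fewer evaluable patients.** Section 10.2 refers to 9 unusable participants. With 70 − 9 = 61 and a 1 SD effect, the rate is 36% at a 50/50 split and 63% at 80/20.

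**Step 4: the interaction test.** In the same simulations, a t test of the treatment-by-stratum interaction was falsely significant in 4.8% to 5.3% of trials, whatever the split or common effect.

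**Step 5: its power.** In SD units, the standard error of the difference between stratum effects is √(2/n₁ + 2/n₂), with n₁ and n₂ per arm. For a true between-stratum difference of 1 SD, by normal approximation:
- 50/50: √(2/17.5 + 2/17.5) = 0.478; 1/0.478 = 2.09; power Φ(2.09 − 1.96) = 55%.
- 80/20: √(2/7 + 2/28) = 0.598; 1/0.598 = 1.67; power Φ(1.67 − 1.96) = 39%.

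**The case against.** The strongest reply is that the plan does not commit the error. The entry is a few words in a table. It names no outcome, test or threshold, and does not say that strata will be compared. Giving an estimate in each stratum is also a stratum-specific analysis and is legitimate. The objectives in section 2 contain no subgroup question, and the primary analysis is the overall regression. All of this stands. A reader might infer that subgroup effects will be declared by setting one stratum's p-value against the other's; the documents do not say so. Nor do they support calling the strata small and unequal as a fact, since no sizes are given.

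The percentages are also conditional. They give the chance of a discordant pair of p-values, not the chance that someone claims a difference. They use unadjusted t tests, whereas the plan intends regression for blood loss. They assume equal arms within strata, although section 10.1 bases randomization on fibroid volume, location and parity. With no true effect the rate is 9.5%, far below the other rows.

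Finally, confidence intervals by stratum let a reader see significance at a glance, so leaving out p-values does not remove the risk. That is fair, and it is why the interaction estimate has to be the main subgroup result.

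What remains is that two factors were chosen for subgroup work, and the only approach named cannot show whether the effect differs between their levels.

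**Conclusion.** The point holds as a minor gap in the analysis plan, conditional on how the stratum results are read. If they are judged separately at 0.05 and the true effect is identical, the chance that exactly one stratum is significant is about 30% to 59% at 1 SD, 49% to 64% at 0.75 SD and 42% to 47% at 0.5 SD, against about 5% for an interaction test. With no effect it is 9.5%, still about twice nominal. These figures rest on all 70 patients being evaluable, two-sided testing, arms balanced within strata, and assumed splits from 50/50 to 80/20. Even the most favorable split gives 30% at the plan's own design effect. The primary comparison of blood loss is not affected.

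**What to change.** In section 10.3, state that effect modification by prior cesarean and by gravid status will each be assessed with a treatment-by-factor interaction term, each in its own extension of the primary linear regression. Separate models are sensible because every woman with a prior cesarean is also gravid, so the two factors overlap. Report each interaction estimate with its 95% confidence interval as the subgroup result. Give the stratum estimates with confidence intervals as description only, and label all of it exploratory.

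The cost is a sentence or two and one extra term in each of two models; no new data are needed. The downside is low power: about 39% to 55% at a total of 70, even for a between-stratum difference as large as the whole design effect. A non-significant interaction would therefore not show that the effect is the same in both strata, and the report should say so.
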